Statistical Analysis Plan

1. Outcome Measures

Primary outcome:

1. 30-day survival in OHCA patients included in the HeartRunner trial.

Secondary outcomes:

1. Bystander defibrillation prior to EMS arrival
2. Bystander cardiopulmonary resuscitation prior to EMS arrival
3. Return of spontaneous circulation at hospital arrival
4. Neurological intact survival at hospital discharge (cerebral performance category score of 1-2)¹
5. 1-year survival

For safety outcomes the secondary outcomes are:

1. Physical injuries or accidents among activated citizen responders
2. Psychological stress or anxiety among activated citizen responders

Physical injuries and psychological stress will be assessed through an electronic survey sent out 90 minutes after activation. Non-responders will be followed up by phone call, text message or e-mail.

2. Power calculations

There was an overall survival of approximately 15% in 2018 in Denmark. Based on prior studies from Stockholm and Holland time to arrival of bystanders decreased by 2.5 minutes with introduction of activated lay persons. Experiences from Sweden have shown that volunteer citizen responders can be recruited and arrive before all dispatched units in 25% of the cases.^{2,3}

This is a superiority trial and sample size and power calculations are based on an assumed effect size using a binary outcome (30-day survival). Data from Danish OHCA cases without introduction of a HeartRunner program showed a decreased chance of survival with increasing EMS response times (30-day survival for all OHCA cases were 12%, 8%, and 4% for EMS response times of <5 minutes, 5-10 minutes, and >10 minutes, respectively).⁴ Similarly, the chance of having a shockable heart rhythm (ventricular fibrillation/pulseless ventricular tachycardia) decreased from 50% within 5 minutes, 30% within 5-10 minutes, and below 20% for EMS response times above 10 minutes.⁴

Estimated 30-day survival chances according to citizen responder response times are: 25% within 3 minutes, 25% within 3-9 minutes, and 4% after 9 minutes.

Power calculations estimated by Fisher's exact test according to time strata are then (using a power (1-beta) of 0.80 and a significance level (alpha, two-sided test) of 0.05): <3 minutes: 536 patients (increase from 15 to 25%) and 3-9 minutes (increase from 15 to 25%): 536 patients.

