In addition to the standard frequentist analysis, to aid interpretation of the results, we will also perform a Bayesian analysis. If the assumptions underlying the design of the trial are found to be substantially incorrect (for example, the proportion of survivors may be lower than was anticipated), the precision of the trial's results may be reduced, which would reduce the chance of any treatment difference reaching the conventional threshold for statistical significance. In this situation, interpretation of the results by clinicians

and decisionmakers will be helped by producing a quantitative summary of the probability that activation of HeartRunners is beneficial, taking into account existing evidence and the trial's results.

Bayesian analyses will be performed to estimate the posterior distribution of the OR and the corresponding 95% credible intervals for each outcome stratified by time stratum.

The Bayesian analysis will model each outcome (primary and secondary) using betabinomial distributions (as the outcomes are binary). The posterior distribution of the odds ratio for each outcome will be estimated. Analyses will use separate priors for the intervention and comparison groups. For the comparison group, a weakly informative prior will be used. For the intervention group, an informative prior based on data from previous studies will be used. Sensitivity analyses will examine the effect of changing the prior distributions.

5. Subgroup Analysis

Since time from cardiac arrest to defibrillation is the most powerful determinant of survival, there may be heterogeneity of the intervention effect between subgroups that inherently differ in time from cardiac arrest to citizen responder intervention due to practical circumstances.⁵ Differences in the primary outcome are therefore anticipated in the following groups:

1. Witnessed OHCA defined as someone (not EMS) sees or hears the person collapse with a cardiac arrest.
2. According to ambulance response time (< 5 minutes, 5-10 minutes, >10 minutes) defined as time from emergency call to arrival of EMS at the OHCA location, not at the patient's side.
4. Cardiac arrests occurring in public settings. Public OHCA will be defined as a cardiac arrest occurring in public buildings, sport facilities, airports, work/office buildings, outdoor locations, and in public transport.
5. Cardiac arrest in residential setting. Residential OHCA will be defined as a cardiac arrest occurring in private homes.

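### An informative historical prior on the intervention arm alone lets a difference in survival level between studies appear as a treatment effect in the Bayesian analysis, in either direction

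*SAP*

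**What the plan says.** SAP section 4 adds a Bayesian analysis to the frequentist one. Its purpose is to give clinicians and decision-makers a probability that activation is beneficial, particularly if the design assumptions fail. The example of such a failure is that "the proportion of survivors may be lower than was anticipated".

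The model is beta-binomial for each primary and secondary outcome, by time stratum, and the odds ratio is derived from the two arm rates. On the priors the section says:

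- "Analyses will use separate priors for the intervention and comparison groups".
- Comparison arm: "For the comparison group, a weakly informative prior will be used".
- Intervention arm: "For the intervention group, an informative prior based on data from previous studies will be used".
- On robustness to these choices, the section offers one general sentence: "Sensitivity analyses will examine the effect of changing the prior distributions".

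The section does not name the earlier studies, the prior means, the prior weights or the alternative priors to be tried.

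**The concern.** Randomisation makes the two arms of this trial comparable with each other. It does not make either arm comparable with patients in earlier studies. A prior on the intervention arm's absolute rate brings in the survival level of those studies, with nothing equivalent on the control side to cancel it. The posterior odds ratio then mixes two things: what the trial shows about activation, and how far the earlier populations differed in prognosis.

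Different levels are realistic. SAP section 2 reports "There was an overall survival of approximately 15% in 2018 in Denmark", and for another Danish data set "30-day survival for all OHCA cases were 12%, 8%, and 4% for EMS response times" rising from under 5 to over 10 minutes. Even the fastest-response group there is 3 points below the 2018 figure. These are not said to be the sources of the prior. They show only that level varies between data sets from the same country.

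The Bayesian result would carry most weight when the primary test is inconclusive, and the SAP's own example of that is a lower survival level than planned. If the historical level lies above the trial's, the model raises the intervention arm only. If it lies below, a real benefit is diluted.

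**Working it through.** **Arm size.** The SAP states no Bayesian figure to reproduce, so its sample size was checked first. With 1:1 allocation (assumed), the two-sided Fisher test at 15% against 25% has exact power 0.802 with 268 per arm, which agrees with the stated 536 in total. The inflation also agrees: 536 / 0.64 / 0.40 = 2093.75, rounded to 2094. Since the analysis is by intention to treat, all true arrests count: 2094 × 0.64 / 2 = 670 per arm and stratum.

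**Model.** Let n = 670, x be the survivors in an arm, m the prior mean and E the effective prior sample size.

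- Control: Beta(1 + x, 1 + n − x), taking Beta(1,1) as the weak prior (assumed).
- Intervention: Beta(mE + x, (1 − m)E + n − x).
- The intervention posterior mean is (mE + x)/(E + n). It moves from the observed rate by E/(E + n) × (m − x/n). The control arm has no matching movement.

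**One case by hand.** Take 100/670 in both arms, m = 25% (the SAP's design value, used only as an example) and E = 300.

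- Intervention: (75 + 100)/970 = 18.0%, odds 175/795 = 0.220.
- Control: 101/672 = 15.0%, odds 101/571 = 0.177.
- Ratio: 0.220/0.177 = 1.24. The posterior median by simulation is 1.25 (95% credible interval 0.96 to 1.63).

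**Equal survival in both arms** (posterior median OR, P(OR > 1)):

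| Observed, both arms | Prior mean | E | OR | P(benefit) |
|---|---|---|---|---|
| 100/670 (15%) | 15% | 50 to 300 | 0.99 | 0.48 |
| 100/670 | 25% | 50 | 1.05 | 0.62 |
| 100/670 | 25% | 100 | 1.10 | 0.74 |
| 100/670 | 25% | 300 | 1.25 | 0.95 |
| 100/670 | 12% | 50 | 0.98 | 0.44 |
| 100/670 | 12% | 100 | 0.96 | 0.40 |
| 100/670 | 12% | 300 | 0.92 | 0.29 |
| 100/670 | 10% | 300 | 0.88 | 0.18 |
| 67/670 (10%) | 10% | 100 or 300 | 0.99 | 0.47 |
| 67/670 | 15% | 100 | 1.06 | 0.63 |
| 67/670 | 15% | 300 | 1.16 | 0.82 |

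With matching levels there is almost no shift. With a gap, the shift follows its sign and grows with E.

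**Frequency under a true null.** In 4000 simulated trials per scenario, with 15% survival in both arms, m = 25% and E = 268, P(OR > 1) exceeds 0.975 in about 39% of trials at 268 per arm and 29% at 670. With m = 10%, it falls below 0.025 in about 16% and 13%. With flat priors each tail is about 2 to 3%.

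**Separating level from effect.** Suppose a hypothetical earlier controlled study with 300 per arm. The one-arm prior uses its intervention arm (E = 300). The alternative uses its log odds ratio with Woolf standard error √(1/a + 1/b + 1/c + 1/d) over the four cells: 0.229, 0.189 and 0.297 for the three cases. The control log-odds has a Normal(−1.75, 2.5) prior.

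| Earlier study | This trial | One-arm prior | Log-OR prior |
|---|---|---|---|
| 15% vs 15% | 67 vs 67 of 670 | OR 1.16, P 0.82 | OR 1.00, P 0.50 |
| 25% vs 25% | 100 vs 100 | OR 1.25, P 0.95 | OR 1.00, P 0.50 |
| 10% vs 7% (OR 1.48) | 127 vs 100 | OR 1.09, P 0.74 | OR 1.36, P 0.99 |

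In the first two rows neither source shows an effect, yet the one-arm prior suggests one. In the third row both sources favour activation, and the trial alone gives OR 1.33, P 0.975. The one-arm prior combines them into weaker evidence than the trial by itself: (30 + 127)/970 = 16.2% against 15.0%. With 100 per arm in the earlier study, the third row gives P 0.92 against 0.98.

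**The case against.** The best counter-argument is that the size is assumed. Every prior mean and weight above is a choice made for this check, and the largest shifts need both a wide gap and a heavy prior. With 15% in both arms, 670 per arm and E of 50 to 100, prior means from 10% to 25% give ORs of only 0.94 to 1.10 and P(benefit) from 0.35 to 0.74. The 3-point gap in the SAP's own figures gives P 0.40 at E = 100. Those Danish figures also come from cases without a responder programme, so they are not a natural source for an intervention prior. All of this stands. It limits what can be said about size, but not the mechanism, which follows from the stated model.

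It is also fair that the analysis is supplementary, that no decision threshold is attached to it, and that Table 1 in SAP section 3 will show the raw proportions. A reader could see that the posterior departs from the data, but not whether effect evidence or survival level caused the departure.

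The planned sensitivity analyses could expose the problem. As worded, however, varying the mean or weight of the one-arm prior would satisfy them and leave the asymmetry in every run.

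Finally, a log-OR prior can also move a null result. One centred on OR 1.89 with SD 0.3 gives OR 1.14, P 0.83 for 15% in both arms. That shift comes from a stated belief about the effect, which readers can judge.

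**Conclusion.** The concern holds. As specified, the main Bayesian result can turn a difference in outcome level between studies into an apparent benefit or an apparent lack of one. The shift is negligible when levels match and modest when the prior is worth 50 to 100 patients. It is large when there is a wide gap and the prior is worth 300: P(benefit) ran from 0.18 to 0.95 on identical survival of 15% in the two arms, for prior means of 10% to 25%.

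These figures assume 1:1 allocation, 670 true arrests per arm and stratum, a Beta(1,1) control prior and undiscounted borrowing at the stated weight. The SAP does not fix the prior parameters, so the actual direction and size cannot be determined from it. The primary analysis is untouched. This is a weakness in a supporting analysis that should be corrected, not a threat to the trial's main conclusion.

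**What to change.** Replace the arm-level priors in SAP section 4 with logit(p_control) = a and logit(p_intervention) = a + d.

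- Put a weakly informative prior on a.
- Put the historical information on d, the log odds ratio, taken from within-study contrasts. Use a weak or neutral prior on d for outcomes that have no such contrast.
- Name a neutral prior, for example Normal(0, 1), and a sceptical prior, for example Normal(0, 0.35), as sensitivity analyses. Print the neutral-prior result beside the informative one. For 127 against 100 survivors of 670 these give P(benefit) of 0.975 and 0.966, so a real signal is retained.
- State the source studies, centre and SD of every prior before outcome data by arm are seen.

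If arm-level priors are kept, state their sources, means and effective sample sizes in advance, and require one sensitivity analysis with the same weakly informative prior in both arms.

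The cost is SAP wording and a slightly different model in standard software, with no effect on patients or data collection. The downside is that earlier studies without a control group could no longer contribute, so the posterior may be less precise. How much is lost depends on which studies the sponsor has in mind.

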Data from the pilot study showed approximately 64% of suspected OHCA were real OHCA. Further, in approximately 40% of cases for which the HeartRunner system was activated, at least 1 citizen responder arrived prior to EMS. It is thus necessary to account for these conditions when calculating power for this study. Thus, for group 1 and 2, 536 cases of true OHCA would be identified among 838 cases of suspected OHCA. To achieve at least 838 suspected OHCA where at least one activated citizen responder arrived prior to EMS, it would require 2094 suspected OHCA. Thus, in total, 2094 suspected cardiac arrests in stratum 1 and in stratum 2 are estimated to be included in the study. Power calculations were performed using the procedure Power (with the twosamplefreq statement based on Fisher's exact test) in SAS version 9.4 (SAS Institute, Cary, NC, USA).

The study is powered to independently address primary outcomes in the 2 time strata according to expected time from activation to arrival of a citizen responder who can assist with resuscitation: <3 minutes (stratum 1) and 3-9 minutes (stratum 2).

3. Statistical Analysis

Eligibility, allocation, inclusion and exclusion are displayed in a trial diagram (Figure 1) and described in section 4 Study Methods in the study protocol version 3. Analysis will be performed following an intention-to-treat principle (patients for whom the HeartRunner system was activated vs. not activated), except for cases excluded as described in subsection 4.6. Baseline characteristics will be summarized as means and standard deviations, medians and interquartile ranges, or frequencies (number, percentages). The following baseline characteristics will be reported for both groups (intervention vs. control): median age, proportion of male patients, proportion with an initial shockable heart rhythm, proportion of witnessed OHCA, proportion of OHCA at home, time of day (8 a.m.-4 p.m., 4 p.m. -12 a.m., 12 a.m.- 8 a.m.), median EMS response time (defined as time from call to vehicle stop at scene), time difference between dispatch of EMS and dispatch of citizen responders, defibrillation performed by EMS, and median distance to nearest AED from the OHCA location.

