The primary outcome (30-day survival) will be reported as proportion of patients surviving 30 days for the intervention and control group. Fisher's exact test will be used to test whether activating the citizen responder system can improve 30-day survival. Results will be presented as a relative risk (RR) with a corresponding 95% confidence interval (95% CI) and a risk difference (RD) with a corresponding 95%

confidence interval (95% CI), Table 1. Survival during the first 30 days will be presented using cumulative survival.²

Analysis of the secondary outcomes (bystander defibrillation, bystander cardiopulmonary resuscitation, return of spontaneous circulation on hospital arrival, and neurological intact survival (cerebral performance category score of 1-2 at hospital discharge), and 1-year survival) will be reported as proportions and compared within intervention groups using Fischer's exact test as described above for the primary outcome.

All tests will be performed independently in the 2 time stratum of the study. As a secondary analysis, data from stratum 1 and 2 will be combined. The combined analysis will be performed using a logistic regression with intervention (yes, no) and time (<3 and 3-9) as fixed effects. An exact test of the effect of the intervention will be performed. Stratum 3 will be described but not statistically analysed since this group is expected to be very small.

The safety outcomes physical injuries and psychological distress and anxiety among the activated citizen responders will be presented by frequency distributions (number, percentages).

Outcome	Intervention N_{OHCA}/N_{survival} (%)	Control N_{OHCA}/N_{survival} (%)	RR (95% CI)	RD (95% CI)	p-value
Primary outcome: 30-day survival					
<3 min					
3-9 min					
>9 min					
Secondary outcome: Bystander defibrillation prior to EMS arrival					
<3 min					
3-9 min					
>9 min					
....					

Table 1. Primary and secondary outcome. RR, relative risk; RD, risk difference; CI, confidence interval; OHCA, out-of-hospital cardiac arrest; EMS, emergency medical services

4. Additional Statistical Analysis

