6. Distance from OHCA to nearest AED (0-250m, 251-500m, 501-1000m, >1000m). Distances will be calculated as straight-line.

A test for interaction in subgroups in relation to the intervention effect (citizen responder activation) will be performed for the primary outcome for the above-mentioned groups. This study is not powered to detect differences in primary outcome between intervention and control arm in the subgroups.

To test whether the effect of the intervention (citizen responder activation) differ significantly between the subgroups for the primary outcome (30-day survival), the interaction between the intervention and subgroup (subgroup-intervention interaction) will be tested. A logistic regression with intervention (yes, no), subgroup and the interaction between intervention and subgroup will be used. The analysis will include stratum 1 (<3min) and stratum 2 (3-9 min) and stratum will therefore be included as fixed effects. An exact test of the subgroup-intervention interaction effect will be performed. Results will be presented as proportion of patients surviving 30 days in the intervention and comparison groups, relative risk (RR) with a corresponding 95% confidence interval (95% CI) and a risk difference (RD) with a corresponding 95% confidence interval (95% CI), Table 1.

6. Statistical stopping criteria

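### Within each subgroup level, the section 5 interaction models assume one intervention odds ratio for both time strata, so a stratum difference in effect could partly appear as a subgroup interaction

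*SAP*

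**What the plan says.** SAP section 5 defines the model for every subgroup: "A logistic regression with intervention (yes, no), subgroup and the interaction between intervention and subgroup will be used". Strata 1 and 2 are analysed together, and for that reason "stratum will therefore be included as fixed effects". The test is described as follows: "An exact test of the subgroup-intervention interaction effect will be performed". No intervention x stratum term is named there, nor in the combined model of section 3.

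Three other statements bear on this:

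- For the main analyses, section 3 keeps the strata apart: "All tests will be performed independently in the 2 time stratum of the study".
- Section 5 chooses its subgroups because it expects "subgroups that inherently differ in time from cardiac arrest to citizen responder intervention due to practical circumstances". The strata are defined in section 2 by the expected time from activation to a responder's arrival (under 3 minutes, 3 to 9 minutes).
- Section 2 powers both strata on the same effect, 15% to 25% survival. Section 5 says the subgroup comparisons are not powered.

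**The concern.** With stratum as a main effect only, the model lets baseline survival differ by stratum and lets the intervention effect differ by subgroup. It does not let the intervention effect differ by stratum within a subgroup level.

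Suppose the shorter-time stratum benefits more and also holds more public arrests, or more arrests near an AED. The public or near-AED level then draws more of its patients from the stratum with the larger effect, and its pooled odds ratio is higher for that reason alone. The interaction test can pick this up with no subgroup effect inside either stratum. With the opposite mix, the same mechanism can hide a real subgroup effect.

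What is at stake is attribution. A location or AED-distance interaction might be reported as a feature of the setting when it partly restates a difference between time strata. No primary conclusion is affected.

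**Working it through.** **1. The plan's own figures.** With 1:1 arms (assumed; the supplied text does not state allocation), two-sided Fisher power for 15% vs 25% is 0.802 at 268 per arm, so 536 is the total for both arms. Then 536/0.64 = 837.5 (838 in the SAP) and 837.5/0.40 = 2093.75 (2094 in the SAP). All reproduce.

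**2. Inputs for the check.**

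- True arrests per stratum: 2094 x 0.64 = 1,340 (section 2).
- Control survival: 15% in both strata (section 2).
- Full effect: 15% to 25% (section 2).
- Diluted intention-to-treat effect: 15% + 0.40 x (25% - 15%) = 19%. This assumes that only cases reached before EMS benefit.
- Subgroup shares by stratum: assumed over a range, because the documents give none.
- True subgroup effect within each stratum: none.
- Test: large-sample, two-sided 5%, in place of the exact test.

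**3. One case by hand.** Public share 50% in stratum 1 and 20% in stratum 2; full effect in stratum 1, none in stratum 2.

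- Stratum 1 odds ratio: (0.25/0.75)/(0.15/0.85) = 1.889, log 0.636. Stratum 2: log 0.
- Stratum 1 makes up 670/(670 + 268) = 0.714 of public arrests and 670/(670 + 1,072) = 0.385 of the others.
- Approximate log interaction: (0.714 - 0.385) x 0.636 = 0.21, an odds ratio of about 1.23. Fitting the planned model to expected counts gives 1.225 (log 0.203), standard error 0.214.
- z = 0.203/0.214 = 0.95. Rejection = P(Z > 1.01) + P(Z < -2.91) = 0.156 + 0.002 = 15.8%. Simulation gave 15.7%.

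With 19% vs 15%, the stratum 1 log odds ratio is ln[(0.19/0.81)/(0.15/0.85)] = 0.285. The fitted interaction odds ratio falls to 1.10 and rejection to 7%.

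**4. Range for public setting.** Rejection by the planned test. Column heads give intervention-arm survival in stratum 1 / stratum 2.

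| Public share, stratum 1 / 2 | 25% / 25% | 19% / 15% | 25% / 20% | 25% / 15% | SE ratio if term added |
|---|---|---|---|---|---|
| 25% / 25% | 5% | 5% | 5% | 5% | 1.00 |
| 30% / 20% | 5% | 5% | 5% | 6% | 1.01 |
| 40% / 20% | 5% | 6% | 6% | 10% | 1.03 |
| 40% / 15% | 5% | 7% | 7% | 13% | 1.04 |
| 50% / 20% | 5% | 7% | 7% | 16% | 1.05 |
| 50% / 15% | 5% | 8% | 8% | 20% | 1.08 |
| 60% / 20% | 5% | 8% | 9% | 24% | 1.09 |
| 70% / 15% | 5% | 12% | 12% | 39% | 1.20 |

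Simulations of 1,500 to 2,000 trials per scenario agree: for 25% / 15%, 14% at shares 40% / 15%, 21% at 50% / 15%, 24% at 60% / 20% and 41% at 70% / 15%.

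**5. AED-distance bands (3 df).**

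- Shares 35/30/20/15% vs 15/25/30/30%: about 6% for 19% / 15%, and 9% to 10% for 25% / 15%.
- Shares 50/30/15/5% vs 10/20/35/35%: 8% to 9%, and 24% to 26%.
- The strongest association in a further set of assumed bands gave 28% for 25% / 15%.

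**6. With intervention x stratum added.** Simulated rejection was 3.6% to 6.9% across scenarios (simulation error about 1.1 points), which is consistent with 5%. An exact conditional test would not remove the problem, because it conditions on the same model without the term.

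**The case against.** A reader might infer that these tests are invalid, or that any location or AED-distance interaction would be an artefact. The documents do not support that, for four reasons.

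- **Both conditions are hypothetical.** The power section assumes the same effect in both strata, and then nothing is inflated. Testing the strata separately does not show that different effects are expected.
- **The association with stratum is inference.** Section 5 speaks of time from arrest to responder intervention, while the strata use expected time from activation to arrival. These are different intervals, and no document says how public setting or AED distance is distributed over the strata.
- **The estimand is not stated.** Section 5 expects heterogeneity because time to intervention differs between subgroups. An interaction that partly reflects time is arguably what it set out to find, and including stratum may be no more than ordinary adjustment when pooling. That the SAP intends a within-stratum subgroup contrast cannot be read from its text.
- **The higher rates need strong assumptions.** They give all 1,340 true arrests in one stratum the full 10-point effect, whereas the sample-size argument ties that effect to the 40% reached before EMS.

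All four stand and limit the point. Two further replies carry less weight. Declaring the subgroups unpowered addresses missed effects, not a bias in the interaction term. Showing primary results by stratum would reveal a stratum difference, but would not show how much of a subgroup interaction it explains.

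**Conclusion.** The point holds as a modest improvement. Within each subgroup level, the planned models impose one intervention odds ratio on both strata. A stratum difference in effect can pass into the subgroup interaction, but only if the subgroup mix also differs by stratum.

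The inflation is nil under the design's own equal-effects assumption and small under a diluted effect. It is material only when a full effect in one stratum, none in the other and marked imbalance coincide. The 70% / 15% mix lies above the main ranges and shows that they are not upper bounds. All rates rest on assumed subgroup shares, 1:1 allocation and a large-sample test, so the true size is unknown.

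**What to change.** In SAP section 5, keep the planned model and add a second fit for each subgroup with these terms: intervention, subgroup, stratum, intervention x stratum, intervention x subgroup. Report its intervention x subgroup test beside the planned one. State in advance that a subgroup interaction will be described as separate from the time strata only if it persists in the second model. The planned model then still shows overall heterogeneity, including any part that runs through time, and the comparison shows how much the strata account for.

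The cost is one extra term in models already planned, with no new data. It uses one degree of freedom and makes the standard error of the subgroup interaction 0% to 10% larger for public shares up to 60% vs 20%, and about 20% larger at 70% vs 15%. The added term deals only with the strata: the listed subgroups can still stand in for one another, and actual arrival times still vary within a stratum.

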Protocol Changes

Changes made from version 2 (published May 14, 2019) to version 3 (December 3, 2020)

- Two new investigators added (title page):
[name], Copenhagen Emergency Medical Services, Ballerup, Denmark
[name], National Institute of Public Health, University of Southern Denmark, Copenhagen, Denmark
One investigator removed (title page):
[name], Copenhagen Emergency Medical Services, Ballerup, Denmark
- Power calculation changed. Baseline survival is increased from 12% to 15% based on data from 2018 from the Danish Cardiac Arrest Registry that has been published recently. Effect estimate for stratum 1 has been decreased from 35% to 25%. The new power calculation, including these new data, results in a sample size of 536 patient for both stratum 1 and 2. Since we are expecting 64% to be true OHCA and a citizen responder only arriving before EMS in 40% of the cases, we will include 2094 patients in stratum 1 and 2094 patients in stratum 2 (section 5.2)
- Length of study changed from 4 years to up to 8 years, and total included patients changed to approximately 4200 because of changes in power calculation (multiple sections)
- New wording for the approval from the Ethics Committee and addition of add-on approvals from the Danish Patient Safety Authority for data collection in 2019 and 2020 (Scientific summary and section 8)
- Secondary outcome. Neurological intact survival will be assessed at hospital discharge through patient's charts, not at 30 days. This is changed in multiple sections and a new data source has been added to section 4.12
- Safety outcome. Psychological impact will not be assessed at 4 weeks but assessed through a survey sent out 90 minutes after activation. Non-responders will be followed-up by phone call, text message or e-mail.
- Stratum 3 will not be included in analyses since this stratum is assumed to be very small.
- One subgroup has been deleted (arrival of citizen responders prior to EMS, since this is not assessable for the control group). The subgroup assessing OHCAs in public and residential settings has been divided up into two separate groups.
- The wording *heart runner* has been changed to *citizen responder* throughout the protocol

- Corrections of grammar and minor typing errors throughout the protocol

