A Data Safety and Monitoring Board with statistical, cardiological and prehospital expertise will follow the study. Formal interim analyses are not planned. This committee is composed of members otherwise independent of the study. They can recommend the steering committee to discontinue the study, but it is the only body which during the course of the study received unblinded results grouped by treatment. The Safety Committee and Monitoring Board will form its own guidelines. The major events to be considered by the safety committee are survival rates (effect) and serious physical injuries or psychological stress among citizen responders (safety). The primary tracking of safety uses a research computer linked directly to the HeartRunner mission server. Using this system, responses can be tracked continuously, and reports can be prepared for the study Data Safety and Monitoring Board. Further, events that come to the attention of study staff and which are not covered by tracking of citizen responder responses and which are either fatal, life threatening, causes hospitalization or lengthening of hospitalization, results in significant or lasting disability or leads to a congenital defect will be reported as well.

7. References

1. Jennett B and Bond M. Assessment of outcome after severe brain damage. *Lancet*. 1975;1:480-4.

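### Does the monitoring board's unblinded view of survival, with no written stopping boundary, undermine the 0.05 significance level?

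*SAP*

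**What the plan says.** SAP section 6 sets up a Data Safety and Monitoring Board, independent of the study, with statistical, cardiological and prehospital expertise. It makes five statements that bear on this point:

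- "Formal interim analyses are not planned".
- The board alone sees unblinded results by treatment during the trial.
- "They can recommend the steering committee to discontinue the study".
- "The major events to be considered by the safety committee are survival rates (effect", followed by serious injury or psychological stress in citizen responders, labelled as safety.
- The board draws up its own guidelines.

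The section names no boundary, schedule of looks or alpha spending.

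SAP section 2 (Power calculations) sizes each time stratum "using a power (1-beta) of 0.80 and a significance level (alpha, two-sided test) of 0.05", giving "<3 minutes: 536 patients (increase from 15 to 25%) and 3-9 minutes (increase from 15 to 25%): 536 patients". The Protocol Changes list adds: "Length of study changed from 4 years to up to 8 years".

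**The concern.** The section is headed as stopping criteria but contains no statistical criterion. A body that compares the primary outcome by arm, treats it as an effect measure and can recommend stopping is doing interim efficacy analysis in substance, whatever name is used. The label on survival makes it harder to read the section as monitoring for harm only. Meanwhile the whole two-sided 0.05 in each stratum is spent on a single final test.

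If the trial stopped early because survival looked better with activation, and no boundary governed that decision, the reported p-value and confidence interval would not have their stated level and the effect would tend to be overestimated. A trial of up to 8 years leaves time for several reviews.

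**Working it through.** **1. Does the plan's sample size reserve any alpha for interim looks?**

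Inputs from SAP section 2: 15% versus 25% survival, two-sided alpha 0.05, power 0.80, SAS Proc Power "with the twosamplefreq statement based on Fisher's exact test". The allocation ratio is not stated; 1:1 is assumed.

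- Exact enumeration of Fisher's two-sided test at 268 per arm (2 × 268 = 536) gives power 0.802, so 536 is reproduced as the total per stratum.
- Inflation for false alarms and late arrivals: 536 / 0.64 = 837.5, rounded to 838; 536 / 0.64 / 0.40 = 2093.75, rounded to 2094. Both match the SAP.

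The sizing uses one look at the full 0.05 and reserves nothing. That agrees with the statement that no formal interim analysis is planned.

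**2. How large could the inflation be?**

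The documents give neither a number of looks (K) nor a trigger. The worst case takes K equally spaced looks, each acted on at nominal p < 0.05. For a normal test statistic, Z_k = (sum of k independent standard normal increments) / √k, and the error is P(|Z_k| > 1.96 for some k ≤ K). From 1,000,000 simulated paths, per stratum:

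| K | two-sided error | false benefit only |
|---|---|---|
| 1 | 5.0% | 2.5% |
| 2 | 8.3% | 4.2% |
| 4 | 12.6% | 6.3% |
| 8 | 17.6% | 8.8% |

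**3. The same worst case with the test the SAP actually plans.**

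SAP section 3 (Statistical Analysis) specifies Fisher's exact test, which is conservative: at 15% survival in both arms and 268 per arm, its actual size with one look is 3.75%. Simulated with repeated Fisher tests at 15% in both arms:

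| Size per arm | K = 1 | K = 4 | K = 8 | false benefit, K = 4 / 8 |
|---|---|---|---|---|
| 268 | about 4% | about 9% | about 12% | 4.5% / 5.9% |
| 670 | about 4% | about 10% | about 14% | 5.1% / 6.8% |

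The second row takes all true arrests among the 2094: 2094 × 0.64 = 1340 per stratum, or 670 per arm.

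**4. What if the board uses an ordinary strict guideline?**

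With interim stopping only at p < 0.001 and the final test at 0.05, the normal-statistic error is 5.0-5.2% for K = 2 to 10. With Fisher's test it is about 3.5-4.6%. Even a looser interim threshold of p < 0.01 keeps the Fisher error at roughly 4-6%.

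**5. Keeping the two strata separate from this point.**

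Two independent tests at 0.05 give 1 − 0.95² = 9.75% with no interim look at all. Combining the strata under the worst case of step 2 gives 1 − (1 − 0.126)² = 23.6% for K = 4 and 1 − (1 − 0.176)² = 32.1% for K = 8. Part of each figure comes from testing two strata, not from monitoring, so the per-stratum figures are the relevant ones.

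**The case for a change.** The strongest case for changing the plan is that the SAP itself classes survival as effect rather than safety, gives the board comparative data and a route to stopping, and prints no rule. Fisher's conservatism does not rescue the worst case: one unadjusted interim look already takes the two-sided error above 5% (6.0% at 268 per arm, 6.8% at 670). A sentence in section 6 would cost almost nothing, and it is hard to show convincingly after the fact which rule applied.

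Much of this stands. The section does not say whether stopping for benefit is allowed, and a reader cannot check a boundary that may exist only in the board's guidelines.

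Three things do not follow, however.

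- The statements do not strictly contradict each other. A trial without formal interim analyses can have an independent board that watches outcomes by arm and may advise stopping.
- Repeated efficacy looks are inferred. The continuous tracking described in section 6 is for safety, through the dispatch server, and no schedule of survival reviews is given. Survival by arm is also the obvious measure of harm to patients, and stopping for harm does not inflate a claim of benefit.
- The worst case needs a board with statistical expertise to recommend ending the trial on nominal p < 0.05. Nothing in the documents points to that.

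**Conclusion.** The concern does not call for a change. Section 6 hands the stopping policy to an independent board that includes statistical expertise, and that board's guidelines are not among the documents. The missing boundary is thus a delegated detail that such a board can fill sensibly. It is not a demonstrated fault in the error control of the final test.

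The size depends on what the board does. Under a strict interim threshold such as p < 0.001, the two-sided error per stratum stays below 5% with the planned Fisher test, and the final 0.05 needs no adjustment. Only if the board acted on nominal p < 0.05 would it rise to about 9-10% with 4 looks or 12-14% with 8. These figures assume equally spaced looks, 1:1 allocation and 15% survival in both arms. If the board makes no recommendation to stop for benefit, monitoring does not raise the error of the final test.

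What remains is a matter of transparency: a reader of section 6 cannot tell which policy the board follows. Stating it there would be tidier, but the planned analysis does not depend on it.
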